4.3 Evaluation Measures and Outcomes

Preoperative assessments along with preoperative and postoperative surveys (assessments described in 4.1 above) regarding quality of life, depression, and anxiety will be obtained from all study participants. Study participants will be followed for approximately 3 months after their scheduled procedure. They will complete follow-up surveys at approximately 1 month and approximately 3 months after surgery by either web-based survey, mail, or via a telephone interview (or in person if the visit coincides with a clinic visit). Collection of falls data will occur approximately monthly for 3 months by phone with study coordinator, or REDCap, or in person. The results of follow-up surveys will be obtained via secure REDCap e-mail link, mail, or telephone survey. Rehospitalizations will be obtained from patient self-report and/or EHR at the end of study follow-up. Please see Table 2.1 for list of outcomes and details.

Additional pre-operative data related to patient medical, social and surgical history, problems, diagnosis and medication lists will be retrieved from the patient electronic health record using the research data core (RDC). Post-operative data including post-operative acute diagnoses (e.g., complications), additional procedures, postoperative opioid use, pain scores will also be retrieved.

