4.3.2.1 Potential Study Primary Outcomes for Planned RCT

Effectiveness outcomes will include the primary outcome measure of PHQ-ADS, a validated composite scale of depression and anxiety symptoms [7] measured at baseline, 1, and 3 months after surgery. The Behavioral Activation for Depression Scale, or BADS (activation subscale), is our primary measure of target engagement. BADS is a sensitive and pragmatic assessment of the mechanism of change in Behavioral Activation. Approximately three months post-operative is the primary endpoint.

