The quantitative data will be used to provide baseline and post-intervention comparisons on a number of outcome variables relevant to the intervention, with the hypothesis that performance on these measures will improve post intervention. These data will also be used to estimate effect sizes for further trials so that these are suitably powered. Quantitative data will be tabulated for descriptive purposes. Given the small sample size, a non-parametric approach will be used to calculate effect size data ($r = Z/\sqrt{N}$), where Z is the standardized test-statistic from a Wilcoxon signed-rank test and N is the sample size, along with the associated 95% confidence interval. The r values will be calculated for the timepoint as compared to baseline.

The observation data will be analyzed using open coding and FRAME analytic framework that helps track any adaptations to intervention bundle and delivery. The interview data will be analyzed using thematic analysis [8].

Table 3. Study Calendar

	Time 0	Baseline/ Time 1	In- Hospital / Post-Op	1 mo follow up	2 mo follow up	3 mo follow up	Post- EOS
Patient Consent	X						
Patient Screening (Appendix A)	X						
Patient Baseline surveys (Appendix D)		X					
Caregiver Consent		X					X
Patient Delirium Assessment (Appendix K) pt UB/ 3-D CAM ; & Caregiver if applicable, FAM-CAM		X (pt)	X(pt) twice daily x 3	FAM- CAM if applicable			

1x weekly for 4 weeks.			days post-op	(weekly x 4wks)			
Patient Follow-up 1 & 3 mo Surveys (Appendix G)				X		X	
Patient Monthly Surveys (Appendix L)				X	X	X	
Patient Post-EOS Surveys (Appendix I)							X*
Patient Semi-Structured Interview (Appendix J)							X*
Caregiver Semi-Structured Interview (Appendix J)							X*
Behavioral Activation and Medication Review Intervention Sessions				Approximately 6-12 sessions as needed (per Pt preference) from Baseline, continuing for up to approximately 3 months post-op during study data collection, until EOS.			

*Post-End of Study (EOS) implementation surveys and semi-structured interviews will be completed approximately 2 weeks after EOS assessment.

6 Patient Participant Retention

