8.1 List of Protected Health Information collected for study

For Patient and Caregiver Participants, the HIPAA-protected identifiers that will be collected for this study include:

- Name
- Date of birth
- Contact information
- Mailing address
- Phone number
- Electronic mail address
- SSN for the purpose of remuneration

For Patient Participants only, these additional HIPAA-protected identifiers will also be collected for study:

- Dates of services (surgical procedure, hospitalization)
- Medical record number

9 Potential Risks

This study involves minimal risk to subjects. Unlikely but potential risks include errors in medication recommendations or medication withdrawal symptoms, and breach of confidentiality. The risk of medication withdrawal (i.e., from benzodiazepines) is mitigated by slowly tapering rather than stopping these medications. Patients who are identified as being acutely suicidal will be excluded from the study. Nevertheless, since the rate of completed suicide in the USA remains high (i.e., about twice the rate of homicide) and most Americans who commit suicide suffer from depression, all participants eligible to participate in this study are statistically at a relatively higher risk for suicide than the general population. However, the participants' absolute risk for completing suicide during this brief study remains very low (i.e., about 1 in 3,000 to 10,000) and participation in the study does not create or increase the risk of completed suicide; rather, most experts believe that one of the most efficient ways to decrease suicidal risk in older depressed individuals is to treat their depression. Furthermore, all participants will be formally assessed frequently throughout the study. If the study personnel identify that a participant has become acutely suicidal, this participant will be referred to a mental health professional for further evaluation and treatment (see section: Procedures to Minimize Risks). This may lead to a clinical intervention that is lifesaving and may not have occurred had the participant not been participating in the study.

10 Adverse Experiences

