Based on the nature of this study, which involves surveys, a cognitive test, and a behavioral intervention, adverse events are exceedingly unlikely. The principal investigator and study coordinator will monitor for breaches of confidentiality and other adverse events on an ongoing basis. If the PI or study coordinator becomes aware of a reportable adverse event, the event will be reported to HRPO according to institutional guidelines.

11 Procedures to Minimize Potential Risks

[name], MD (PI on the Center for Perioperative Mental Health; Co-I on this study) will manage the oversight of the interventions making medication optimization recommendations to reduce the risk of medication error or medication withdrawal symptoms. Algorithms for tapering medications that should not be abruptly discontinued will be employed. We have carried out this deprescribing protocol in several large RCTs and have not seen any problems occur.

Suicide Risk Management: As discussed above, at each assessment point, the research staff will assess for passive death wish, and suicidal ideation, intent or plan when they administer the PHQ-ADS. If a participant endorses suicidal ideation, intent, or plan, the rater will be trained to follow an operationalized protocol (Appendix E) that has been developed to manage high-risk participants in other studies of depressed participants potentially at risk for suicide. This protocol has already been used successfully by [name] team to manage acutely suicidal patients. Briefly, the protocol entails a specific determination of the suicidal risk and prescribes a set of actions. If a participant is determined to be at high and immediate risks, the rater is instructed to stay with the participant until he or she has contacted a study psychiatrist ([name]) to discuss the situation and to devise a plan. In case of extreme emergency, raters are instructed to call their hospital security team or 911 for immediate help and to initiate commitment proceedings.

Patients will be encouraged to check with their physician if there is any question about the safety of any physical activities that are included in the behavioral activation plan. It is possible that the participant may feel uncomfortable completing the surveys or participating in the study sessions. The study sessions and interview can be discontinued at any time, and the patient may refuse to answer any questions that s/he does not wish to answer.

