The study principal investigator and study coordinator will monitor for breaches of confidentiality and other adverse events on an ongoing basis. Once the PI or study coordinator becomes aware of a reportable adverse event, the event will be reported to HRPO and QASMC according to institutional guidelines. This study does not require QASMC audit or submission of DSM reports.

13 Premature Discontinuation

Subjects will be withdrawn if the investigator decides that discontinuation is in the best interest of the subject, or the subject requests withdrawal from the study. As part of the informed consent process, patients will be notified they may choose to not participate in the study or withdraw at any time with no penalty, and no effect on the standard care they receive.

14 Potential Benefits of the Proposed Research to Participants and Others

Although the study is designed to improve symptoms of depression and anxiety and other outcomes of care, there is no guarantee that the study participants will receive any clinical benefits by participating in the study. This may lead to a clinical intervention that is lifesaving and may not have occurred had the participant not been participating in the study. Given the undertreatment of depression and anxiety in older adults, the minimal risks are acceptable in comparison to the potential benefits in improving the mental health of older adults undergoing surgery.

15 Remuneration

It will not cost the patient anything to participate in the study, and with the flexible design allowing for phone visits, they will not be required to make any extra study visits to the medical center (some visits may be concurrent with a clinic or procedure appointment). Patients will receive remuneration by debit card of \$25 for completion of each data collection study visit at Baseline, 1, 2, 3 month post-op, Post-EOS data collection surveys, and semi-structured interview, up to \$125 after completion of their participation.

16 Funding

The study is funded by the National Institute of Mental Health (NIMH) (P50 MH122351-01A1).

17 References

1. Mangusan, R.F., et al., *Outcomes associated with postoperative delirium after cardiac surgery*. Am J Crit Care, 2015. **24**(2): p. 156-63.
2. Blumenthal, J.A., et al., *Depression as a risk factor for mortality after coronary artery bypass surgery*. Lancet, 2003. **362**(9384): p. 604-9.

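### Section 13 does not separate stopping the bundle from leaving follow-up, so the 3-month PHQ-ADS of patients whose bundle is stopped may be lost and the effect size in Section 5 may be biased

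*Combined protocol and SAP*

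**What the plan says.** Section 13 (Premature Discontinuation) states: "Subjects will be withdrawn if the investigator decides that discontinuation is in the best interest of the subject". The same sentence goes on to cover a subject who asks to leave the study, so both routes share one consequence. No category covers a patient who stops the bundle but stays in follow-up.

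Section 11 adds, for patients: "The study sessions and interview can be discontinued at any time". It does not say what then happens to the outcome surveys.

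On follow-up, Section 4.3 says: "Study participants will be followed for approximately 3 months after their scheduled procedure". Section 4 says much the same of all consenting patients. Neither section makes an exception for a withdrawn subject, and neither says that a withdrawn subject is still followed.

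Section 4.3.2.1 names PHQ-ADS as the primary effectiveness measure and adds: "Approximately three months post-operative is the primary endpoint". Section 5 analyses change with a Wilcoxon signed-rank statistic, r = Z/√N: "The r values will be calculated for the timepoint as compared to baseline". It gives no analysis set and no method for missing data, and it says the effect sizes will be used to power further trials. Table 2 makes completeness of PHQ-ADS collection the secondary feasibility outcome and does not say whether withdrawn patients stay in its denominator.

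**The concern.** Stopping an intervention and ending outcome measurement are different events. A rule that merges them can discard outcome data that could still be collected, and the patients concerned are unlikely to be a random subset, because they are chosen on a judgement about their own interest.

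This bears on three parts of the plan. The signed-rank statistic needs a baseline and a follow-up value from the same patient, so an unassessed patient contributes nothing. The study has a single arm, so no comparison group would reveal or offset selective loss. The resulting effect size serves Objective 2 and is carried into the sizing of later trials.

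The completeness outcome would also become harder to read. It could not tell patients who could not be reached from patients the study itself stopped contacting.

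**Working it through.** **Step 1: what the text settles.** The passages, set side by side:

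- Section 13: an investigator-decided stop leads to withdrawal. What is discontinued is not defined.
- Section 11: sessions can be stopped by the patient. Later surveys are not mentioned.
- Sections 4 and 4.3: follow-up lasts about 3 months for all participants. The status of a withdrawn subject is not mentioned.
- Section 5: paired analysis, with no missing-data rule.

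The ordinary operational reading of withdrawal is that surveys stop. That is an inference, because no supplied section says so and none says the opposite.

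**Step 2: the plan's own figures.** Section 3 gives up to 12-15 patients in each of 3 cohorts and up to 45 in total, and 3 × 15 = 45 agrees. The plan states no PHQ-ADS standard deviation, expected change, dropout rate or number of withdrawals, so there is no published figure to reproduce. What follows is illustration.

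**Step 3: effect on r if the patients lost had worsened.** Inputs:

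- N = 45 (Section 3, the maximum).
- Normal changes with SD 7 points and true mean improvement of 2 or 0 points (assumed).
- k patients removed at random from those who worsened (assumed).
- r = Z/√(number of pairs), averaged over 4,000 simulated datasets per setting.

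| Lost (k) | r, true improvement 2 | r, true change 0 | Highest possible completeness, (45 − k)/45 |
|---|---|---|---|
| 0 | 0.27 | 0.00 | 100% |
| 3 | 0.34 | 0.06 | 42/45 = 93% |
| 5 | 0.40 | 0.11 | 40/45 = 89% |
| 7 | 0.46 | 0.16 | 38/45 = 84% |

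Smaller losses matter less: with a true improvement of 2 points, 1 lost gives 0.30 and 2 lost give 0.32. In that setting about 17 of 45 patients worsen, so 7 losses would mean removing 7/17 = 41% of them. The sampling SD of r is about 0.14, so the shift with 3 lost (0.34 − 0.27 = 0.07) is about half of one sampling SD.

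**Step 4: dependence on who leaves.** This is a separate simulation with N = 45, true improvement 0.3 SD (0.3 × 7 = 2.1 points on the scale above) and 1,500 runs per setting. It gives r for all 45 patients, then after the loss:

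| Who is lost | 4 lost | 7 lost |
|---|---|---|
| Random | 0.283 → 0.284 | 0.282 → 0.284 |
| Drawn from those who worsened | 0.283 → 0.382 | 0.286 → 0.469 |
| The worst changes | 0.287 → 0.466 | 0.281 → 0.581 |
| Drawn from above-median improvers | 0.281 → 0.205 | 0.281 → 0.134 |

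The sign and the size of the bias both depend on the withdrawal mechanism, which the documents do not describe.

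**Step 5: the primary outcome.** Section 4.3.1 defines reach of the bundle as completers divided by those who agreed. A patient whose bundle is stopped is a non-completer whether or not surveys continue, so reach does not change.

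**The case against.** A reader might infer that patients who worsen or start outside treatment will be taken off the bundle. The documents do not say so. For the one worsening event they describe, acute suicidality, Section 9 says "this participant will be referred to a mental health professional for further evaluation and treatment". Neither Section 9 nor Section 11 mentions withdrawal. Section 4.2.1 lets the timing, format and frequency of sessions adapt to the patient's needs, which points to adjustment rather than removal. This stands: worsening as a reason to stop is conjecture.

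A reader might also infer that such patients certainly leave the 3-month PHQ-ADS. Sections 4 and 4.3 follow everyone without exception, Section 6 distinguishes data collection visits from intervention visits, and Section 15 pays for data collection visits rather than sessions. The consent form (Appendix C) and the suicide-risk protocol (Appendix E) are not in the supplied text and might settle the matter. This stands in part. Loss of follow-up is not established, but the main text leaves it open, and the wording of Section 13 leans towards it.

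A third inference is that the bias must run towards improvement. It need not, since patients who would have done well, for example on treatment elsewhere, may also leave, and random loss gives no bias. The counts, the SD and the restriction of losses to patients who worsened are all assumed. This stands in full.

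Finally, this is a feasibility study whose primary outcome is untouched. That limits the seriousness. It does not remove the gap, because Section 5 still carries r forward to later trials.

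**Conclusion.** The concern holds in a conditional form. Section 13 offers only withdrawal after an investigator-decided stop, and no supplied section keeps such a patient in outcome follow-up. If surveys then end and the loss is related to symptom course, the paired change and r are biased, in a direction set by who leaves.

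The illustrated shift of r from about 0.27 to 0.34 or 0.40 rests wholly on the assumptions in the working (45 patients, SD 7, true improvement 2 points, 3 or 5 losses, all among patients who worsened). It shows what a few selective losses can do in a sample of this size and does not predict what will happen. The point is a worthwhile, low-cost improvement to the plan. It does not threaten the feasibility conclusion on reach.

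**What to change.** In Section 13, with matching consent wording, define two categories:

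- **Bundle stopped**, by the investigator or by the patient's choice. The patient stays in the study and is still asked for the 1- and 3-month PHQ-ADS and BADS unless they decline data collection.
- **Withdrawn from the study**, used only when the patient withdraws consent to data collection.

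In Section 5 and Table 2, include patients whose bundle was stopped in the baseline comparisons, keep all enrolled patients in the completeness denominator, and report the number in each category with reasons. Give the number of pairs beside each r.

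The cost is a few sentences and the consent wording, plus a few survey contacts with patients no longer in sessions. Section 4.3 already schedules these surveys by web, mail or telephone. The change estimate may turn out less favourable. Nothing here alters who is stopped or how they are treated, which is a clinical matter outside this point.
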